8.4.2 Extraocular muscle function test

Extraocular muscle function testing examines the function of the eye muscles. This test observes the movement of the eyes in six specific directions to evaluate weakness or other problems in the extraocular muscles. The subject will be asked to sit or stand with their head up and looking straight ahead. The assessor will hold a pen or other object approximately 16 inches in front of the subject's face. The assessor will then move the object in several directions and ask the subject to follow it with their eyes, without moving their head. Normal or Abnormal will be recorded in the source documentation and eCRF. Changes in movement of the eyes during the course of the study should be reviewed and assessed by the Investigator for a potential adverse event.

8.4.3 Confrontation visual field

The Confrontation Visual Field test will be used to assess the subject's peripheral vision. The examiner will sit facing the subject, about 3 to 4 feet away from the subject and ask the subject to fix their gaze on the examiner's eye. The examiner will hold their arms straight out to the side and bring their hands into the subject's visual field from the sides in each quadrant. The subject will signal as soon as the hand is seen. Results will be recorded as normal or abnormal in the source documentation and eCRF. Changes in the visual field of the eyes during the course of the study should be reviewed and assessed by the Investigator for a potential adverse event.

8.5 Other safety assessments

At all physical visits, a study staff member who is qualified by training and experience to perform safety assessments, will assess each subject's cheek sensation; firmness and symmetry; and mass formation. After treatment with the study product, product palpability will be performed at each physical visit.

8.5.1 Cheek sensation

Cheek sensation will be tested at all physical study visits using two methods:

1) Monofilament test - assessing the subject's ability to feel the sensation of a 0.4G monofilament on 3 points on right and left cheek *and*

2) Cotton Wisp test - assessing the subject's ability to feel the sensation of a cotton wisp on 3 points on the right and left cheek. The 3 different points on each side will be tested randomly.

Subjects will be blindfolded and asked to acknowledge sensation or lack of sensation at each point. Any lack of sensation should be further assessed by the Investigator for confirmation of any potential adverse event.

8.5.2 Cheek firmness, symmetry and function

At all physical visits, a study staff member who is qualified by training and experience to perform safety assessments will assess each subject's cheek firmness, symmetry (with face at rest and with eyes tightly closed), and function (puff cheeks, broad smile, and chewing motion). These parameters will be rated as "Normal" or "Abnormal." Any abnormal result should be further assessed by the Investigator for confirmation of any potential adverse event.

8.5.3 Mass formation

Mass formation in the cheeks will be assessed by a study staff member that is qualified by training and experience to perform safety assessments at screening/baseline and at all physical visits. Mass formation will be defined as lumps or aggregation of coherent material. An assessment of mass formation is to be recorded as an adverse event.

8.5.4 Device palpability- only for subjects in the treatment group

Device palpability will be assessed at each scheduled post-treatment visit and will assess whether or not the palpability is the normal expected feel. An unexpected feel is to be recorded as an adverse event.

8.6 Adverse events

8.6.1 Definition of an adverse event

An AE is any untoward medical occurrence, unintended disease or injury, or untoward clinical signs (including abnormal laboratory findings) in subjects, users or other persons¹, whether or not related to the study product.

This definition includes:

- a) events related to the investigational product or the reference product
- b) events related to the procedures involved

8.6.2 Definition of a serious adverse event

A serious adverse event (SAE) is an AE that:

- a) led to death,
- b) led to serious deterioration in the health of the subject, that either resulted in
 - 1. a life-threatening² illness or injury, or
 - 2. a permanent impairment of a body structure or body function, or

¹ For users or other persons, this definition is restricted to events related to the investigational product.

² The term "life-threatening" in the definition of "serious" refers to an event in which the patient was at risk of death at the time of the event; it does not refer to an event, which hypothetically might have caused death if it were more severe. (Source: ICH-E2A clinical safety data management: definitions and standards for expedited reporting).

👶 GALDERMA

Effective date: 2021-03-24 11:04

- 4. medical or surgical intervention to prevent life-threatening illness or injury or permanent impairment to a body structure or a body function,
- c) led to fetal distress, fetal death, or a congenital abnormality or birth defect

In cases of doubt, whether an AE fulfils a serious criterion or not, there should be a predisposition to report as a SAE rather than not report as such (see Section 8.6.5).

Definition of unanticipated adverse effect 8.6.3

An unanticipated adverse device effect is any serious adverse effect on health or safety or any lifethreatening problem or death caused by, or associated with, the investigational product, if that effect, problem, or death was not previously identified in nature, severity, or degree of incidence, or any other unanticipated serious problem associated with a device that relates to the right, safety or welfare of the subject (see US requirement CFR 812.3 (s).

Recording instructions 8.6.4

Each subject with an AE occurring after enrollment through study exit should be fully recorded in the source document(s) for further transcription into the eCRF. Each subject should be questioned about AEs at each study visit following randomization and treatment. . The question asked should be:"Since your last clinical visit; have you had any health problems?" Information on AEs can also be obtained from signs and symptoms detected during each examination or from a laboratory test, observations made by the study site personnel, subject diaries, or spontaneous reports from the subjects or their relatives.

When an AE is related to a device deficiency (refer to Section 8.7), including technical device malfunction, the AE shall be recorded on the AE form/module in the eCRF and the technical complaint shall be reported separately on the clinical study complaint form, provided separately in the investigator file, and the eCRF.

Investigators, or other study site personnel, shall record all AEs in the eCRF, including:

- a) Event term (recorded in standard medical terminology and avoiding abbreviations)
- b) Affected area
- c) Start date (first day with symptoms)
- d) Stop date (last day with symptoms)
- e) Intensity (mild, moderate, or severe according to definition in Section 8.6.4.1)
- f) Seriousness (serious or not serious, according to definition in Section 8.6.4.2)
- g) Causal relationship to study product or study product injection procedure (yes or no)
- h) Action taken (none, medication treatment, non-pharmacological treatment, or other procedures/tests, subject withdrawn)
- i) Outcome of the AE (ongoing, recovered, recovered with sequelae, death, chronic/ stable, not recovered at the end of the study)

The pre-defined, expected post-treatment events shall be assessed separately. These events shall be collected daily by subjects in a diary for up to 28 days after each treatment.

³ Planned hospitalization for a pre-existing condition, or a procedure required by the CSP, without serious deterioration in health, is not considered a SAE. (Source: ISO14155:2011).

8.6.4.1 Intensity

Intensity will be recorded for each reported AE. The following definitions of intensity are to be used:

Mild: Awareness of symptoms or signs, but easily tolerated (acceptable)

Moderate: Enough discomfort to interfere with usual activity (disturbing)

Severe: Incapacity to work or to do usual activity (unacceptable)

If the intensity changes within one day, the maximum intensity of the AE during that day shall be recorded.

8.6.4.2 Causal relationship and seriousness

Each AE, serious as well as non-serious, shall be assessed by the Investigator for causal relationship with the study product and its use (the injection procedure) and for seriousness (Yes or No) of the event.

A two-point scale (Yes or No response) shall be used for the causality assessments. The Investigators shall be asked to indicate a response to each of the following questions in the eCRF:

- "Do you consider that there is a reasonable possibility that the event may have been caused by the study product?", and
- "Do you consider that there is a reasonable possibility that the event may have been caused by the study product injection procedure?"

If any of these questions is answered Yes, the AE is considered related.

Each AE will also be assessed for causal relationship and seriousness by the Sponsor, in order to fulfil regulatory requirements.

8.6.5 Reporting of adverse events

Adverse event reporting on each subject shall start upon enrollment (i.e. randomized and/or treated) in the study. Any events that occur after the subject signs the ICF but before enrollment will be recorded in the subject's medical history.

The reporting shall continue during each follow-up visit (including telephone contacts and extra visits between planned visits) until the last scheduled visit in the study.

All AEs, non-serious as well as serious, are to be reported as an AE in the eCRF.

8.6.6 Reporting of adverse events of special interest (AESIs)

All incidences of visual disturbances, regardless of relationship to study product or seriousness, are considered Adverse Events of Special Interest (AESIs) and include but are not limited to the following: any loss of vision, blurry vision, double vision, pain in or around the eye, blind spot or shadow in the visual field, trouble moving eyes.

AESIs should be reported (using the AE Clarification Form) within 24 hours of awareness to the Contract Research Organization (CRO) at the email address **CCI** In case of difficulty to obtain all the required information within 24 hours, an initial report can be submitted with follow up information provided within 24 hours of awareness of the new information.

The following information should be provided when reporting an AESI:

- Subject identification (subject number and initials)
- Event description including observed symptoms
- Medical history related to event

- Event onset date and time
- Depth of injection
- Interventions implemented to treat event
- Event outcome (with resolution date and time if applicable)
- Relatedness to study product or procedure
- Seriousness of event
- Study treatment information (number of injections, date of injections, name of product injected, batch number/lot number, volume injected, injection depth etc.)

If the Investigator assesses an AESI to be serious, an SAE report should be submitted as specified in Section 8.6.7.

Upon receipt of the AESI report, the Medical Monitor and Sponsor will review the information provided, assess the event, and report to the RA, as applicable. The investigator is responsible for reporting events to the IRB per the IRB reporting guidelines.

8.6.7 Reporting of serious adverse events

The Investigator shall report any **SAE** to the CRO **immediately but not later than 24 hours of awareness of the event**. This initial report can be made via e-mail or submitted via the eCRF.

In case of difficulty to obtain all the required information within 24 hours, an initial report can be submitted, with the following information as a minimum, irrespective of whether some of it is regarded as preliminary:

- CTN 43USSA1812
- Subject identification (age, gender, subject number)
- Date when AE occurred
- Date when AE became serious
- Adverse event description
- Name of investigator and original reporter (if other than Investigator)
- Name of study product (investigational product or no-treatment)
- Treatment specification

Follow-up information and data missing in the initial SAE reporting shall be gathered as soon as possible and reported to the CRO, immediately but not later than 24 hours of awareness of the new data. Complete and adequate information on each SAE is required. All attempts to obtain this information, including dates for follow-up activities, must be documented by the Investigator.

Supporting documentation to be provided with the SAE report:

- Concomitant therapies form/list
- AE form/list
- Medical history form/list
- Any other relevant supporting documentation (e.g. hospital notes, death certificate, autopsy reports etc.)

E-mail for SAE reporting:

The SAE form must be signed and dated by the Investigator. If the initial 24-hour SAE report does not contain full information or if it is made without using the SAE form the fully completed and signed SAE form shall be e-mailed to the CRO. A copy of the fully completed SAE form shall be kept at the site. The blinded evaluator should perform live effectiveness assessments only and not discuss the treatment or any potential adverse events with the patient.

In addition, the PI shall report SAEs to the responsible IRB without undue delay. The PI is responsible for checking what reporting procedures are applicable for his/her IRB regarding SAEs and final report of the outcome of the study and to comply with such reporting procedures during the study period.

The Sponsor is responsible for reporting to the RA, if applicable and according to national regulations.

8.6.8 Stopping Rule

Enrollment and injections at an investigational site will be temporarily halted if an SAE occurs for a vascular embolic event that leads to skin necrosis, vision loss, or stroke and is determined by the Investigator to be directly or possibly related to the investigational device or injection procedure. The SAE will be investigated by the Sponsor.

If the Sponsor's investigation concludes:

- The SAE was unanticipated, directly related to the investigational product or device injection procedure, and presents an unreasonable risk to study subjects, enrollment and/or injections will be immediately suspended for all study sites until the event can be properly characterized and an appropriate treatment strategy is established to prevent recurrence of the unanticipated event. All Investigators will be notified of the suspension. The IRB and RA will also be notified.
- If the SAE does not meet the above criteria, then enrollment and injections in the study will continue.

8.6.9 Reporting of unanticipated adverse device effects

The Investigator shall submit to the sponsor and to the reviewing IRB a report of any unanticipated adverse device effect occurring during the study as soon as possible, but in no event later than 10 working days after the investigator first learns of the effect (see US requirement 21 CFR 812:150 (a.), for contact details, see section 8.6.7.

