Assessments for visual disturbance have been implemented at baseline, all treatment and all follow-up visits with specific instructions to immediately see an ophthalmologist or retina expert should any visual disturbance event occur. Moreover, only study Investigators qualified by education and experience, and who are skilled in the use of soft tissue fillers from their clinical practice and involvement in clinical research, and with a firm knowledge of the vascular anatomy and understanding of the depth and plane of injection as well as knowledge of the signs and symptoms and management of potential complications, will be chosen in order to assure proper device implantation and management of study risk.

For intravascular complications or embolic events, the treating physician should provide prompt medical attention and follow relevant clinical practice guidelines ($\underline{8}$) for handling these symptoms. The treating physician should also review the Intravascular Treatment Protocol provided separately as a supportive tool.

Lidocaine can, in rare cases, give allergic reactions, and therefore subjects with known allergy or hypersensitivity to local anesthetics should not be included in the study.

Additional information about reported AEs and anticipated risks are included in the study Instructions for use (IFU) and ROPI.

Stopping rules for the study are included in section 8.6.8.

Given the anticipated low level of acceptable AEs in connection with the injection, the protocol required safety assessments it was determined the risk-benefit assessment for use of Sculptra Aesthetic with the investigational plan specified reconstitution and injection procedures for correction of cheek wrinkles appears to offer a clinical benefit at reasonable risk.

3 Objective(s) and Endpoint(s)

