The aim is to submit the results of this study for publication in the public database ClinicalTrials.gov and to a medical journal for a first joint publication of the results. Everyone who is to be listed as an author of the results of this multicenter study shall have made a substantial, direct, intellectual contribution to the work. Authorship will be based on (1) substantial contributions to the conception or design of the work; or the acquisition, analysis, or interpretation of data for the work; and (2) drafting the work or revising it critically for important intellectual content; and (3) final approval of the version to be published; and (4) agreement to be accountable for all aspects of the work in ensuring that questions related to the accuracy or integrity of any part of the work are appropriately investigated and resolved⁵. Conditions 1, 2, 3, and 4 must all be met in order to be designated as author. Those who do not meet all four criteria will be acknowledged. Among the authors that fulfil the above mentioned criteria, one author will be appointed by Q-Med AB to take primary responsibility for the overall work as primary author.

15 Suspension or Premature Termination

The Sponsor will suspend or terminate the study when so instructed by the IRB or RA, or if it is judged that the subjects are subjected to unreasonable risks, or for valid scientific or administrative reasons, or for business reasons.

The Sponsor may also decide to close a single study site due to unsatisfactory subject enrolment or non-compliance with the CIP, GCP, or applicable regulatory requirements.

In the event of premature termination, Q-Med AB will provide information on the handling of currently enrolled subjects who have not completed the study.

⁵ Defining the role of authors and contributors, compiled by the International Committee of Medical Journal Editors (ICMJE) (http://www.icmje.org).

16 References

1. WMA Declaration of Helsinki

https://www.wma.net/policies-post/wma-declaration-of-helsinki-ethical-principles-formedical-research-involving-human-subjects/

- 2. Sculptra Aesthetic Instructions for Use http://www.galdermausa.com/IFU/Sculptra Aesthetic IFU.pdf
- Vleggaar; Fitzgerald, Lorenc et al.Consensus recommendations on the use of injectable Poly-L-Lactic-Acid for facial and non-facial volumization. Journal of Drugs in Dermatology 2014; 13 (4): 44-51
- 4. GLI.04.SPR.US10321 Sculptra PAS 2-yr Clinical Study Report; data on file MA-39427.

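### Stopping rule 8.6.8 requires three joint conditions for study-wide suspension, while section 15 already requires suspension or termination on unreasonable risk alone

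*Protocol*

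**What the plan says.** Protocol 8.6.8 works in two steps. First, a site is temporarily halted when a vascular embolic SAE leads to necrosis of the skin, loss of vision or stroke and "is determined by the Investigator to be directly or possibly related to the investigational device or injection procedure". The Sponsor then investigates.

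Second, the outcome of that investigation decides what follows. All sites are suspended if the Sponsor concludes: "The SAE was unanticipated, directly related to the investigational product or device injection procedure, and presents an unreasonable risk to study subjects". That suspension brings notice to all Investigators, the IRB and the regulatory authority. It lasts until the event has been characterized and "an appropriate treatment strategy is established to prevent recurrence of the unanticipated event". In every other case the second bullet applies: "If the SAE does not meet the above criteria, then enrollment and injections in the study will continue".

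Protocol section 15 (Suspension or Premature Termination) is general. It begins "The Sponsor will suspend or terminate the study when so instructed by the IRB or RA" and goes on "or if it is judged that the subjects are subjected to unreasonable risks". It sets no condition on whether the harm was known beforehand or how closely it was related to the device.

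Section 2.4 directs the reader to one place only: "Stopping rules for the study are included in section 8.6.8".

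**The concern.** The three conditions in the first bullet of 8.6.8 are joined by *and*, so failing any one of them leads to the second bullet, which has no exception for unreasonable risk. An embolic SAE that the Sponsor has just found to be an unreasonable risk, but which was anticipated or only possibly related, therefore falls under an instruction to continue. Section 15 gives the opposite instruction for the same finding. Both are worded as mandatory, and neither says which prevails.

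The case is not contrived. Section 2.4 already lists impaired vision, blindness, stroke and necrosis of the skin as reported consequences of intravascular filler injection. These are the outcomes that trigger 8.6.8, so the condition that the SAE be unanticipated can plausibly fail for the very events the rule was written for.

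The relatedness condition is also hard to apply. Section 8.6.4.2 records causality as Yes or No to a question about reasonable possibility. The form has no grade separating direct from possible, yet in 8.6.8 that difference can decide between suspending the study and continuing.

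What is at stake is subject safety. Treated subjects may have up to four sessions (6.5.2), the outcomes can be permanent, and there is no data monitoring committee (10.7). The decision to resume injections should turn on whether the risk is acceptable.

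**Working it through.** There is no planned figure to reproduce; the check is of wording.

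**Step 1. All combinations.** Three yes/no conditions give 2 × 2 × 2 = 8 combinations. The first bullet of 8.6.8 suspends all sites in 1 of them; the second bullet continues in the other 8 − 1 = 7. Risk is unreasonable in 2 × 2 = 4 of the 8.

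**Step 2. The four combinations with unreasonable risk.**

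| Unanticipated | Directly related | 8.6.8 read alone | Section 15 | Agree? |
|---|---|---|---|---|
| Yes | Yes | Suspend all sites | Suspend or terminate | Yes |
| Yes | No | Continue | Suspend or terminate | No |
| No | Yes | Continue | Suspend or terminate | No |
| No | No | Continue | Suspend or terminate | No |

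The sections conflict in 3 of 4.

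**Step 3. Can the conflicting rows arise?** The rows without direct relatedness can, because the site halt accepts possible relatedness while the first bullet does not. The anticipated rows can, because 2.4 names the trigger outcomes as already reported. Section 8.6.3 narrows the anticipated rows: it treats an effect as unanticipated if its nature, severity or degree of incidence had not been identified before. If the word has that meaning in 8.6.8 (an assumption, since 8.6.8 does not cite 8.6.3), an event worse or more frequent than known still reaches the suspending bullet. What remains is an event of known kind, severity and incidence newly judged unreasonable, or one only possibly related and judged unreasonable.

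**Step 4. Frequency.** The documents describe these events as rare and give no rate. Section 8.6.13 places the list of anticipated events in the study IFU, which was not available. The frequency of the conflict therefore cannot be estimated. For scale only, one can ask how often 8.6.8 would be invoked at all. With about 100 treated subjects, an *assumed* independent per-subject risk p of a trigger SAE, and probability of at least one event 1 − (1 − p)^100:

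- p = 1 in 10,000: 1 − 0.9999^100 = 1.0%
- p = 1 in 2,000: 1 − 0.9995^100 = 4.9%
- p = 1 in 1,000: 1 − 0.999^100 = 9.5%

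These figures describe the trigger, not the conflict, and are only as good as the assumed p. The conflict can arise only in some of those cases.

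**The case against.** The strongest reply is that the protocol is one document. The Sponsor investigates under 8.6.8 and the Sponsor acts under section 15. A Sponsor that has concluded the risk is unreasonable has met the condition of section 15, which is mandatory. On that reading 8.6.8 governs only the release of a temporary halt, section 15 governs the study throughout, and all that is missing is a cross-reference. In addition, section 8.6.7 has the PI report SAEs to the IRB without undue delay, whether anticipated or not, and section 15 binds the Sponsor to any IRB or regulatory instruction. Section 2.4 also judged that the planned use "appears to offer a clinical benefit at reasonable risk" with these rare events in view.

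Most of this stands, and it limits the point. A reader might infer that the protocol compels further injections after an unreasonable risk has been found. It does not: section 15 forbids that. A reader might also infer that every trigger event counts as anticipated, so that the suspending bullet can never operate. The 8.6.3 definition and the unseen IFU do not allow that conclusion.

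What does not stand is that nothing needs changing. The specific rule contradicts the general one without a precedence clause, and the risk section sends readers only to the specific rule. One could read the second bullet as covering only SAEs that meet none of the three conditions. That is not the ordinary reading, and it would leave partly met cases with no instruction in 8.6.8.

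**Conclusion.** The concern holds as a narrow internal conflict in a subject-safety rule, and it should be corrected. The count of three in four describes logical combinations and must not be read as a probability. The conclusion rests on the ordinary reading of the three conditions as all required; it does not depend on any assumed event rate. The protocol as a whole does not direct continuation in the face of unreasonable risk. The defect is that the section written for embolic harm does so when read alone, and depends on another section to correct it. The trial's endpoints, power and data are unaffected.

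**What to change.** Amend 8.6.8 as follows.

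- **First bullet.** Make unreasonable risk sufficient for any SAE that the Sponsor's investigation finds directly or possibly related to the product or the injection procedure, whether or not it was anticipated. Keep the immediate all-site suspension and the existing notifications. In the condition for resuming, refer to recurrence of the event, without the word unanticipated.
- **Second bullet.** State that otherwise, and subject to section 15, enrollment and injections continue.

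An SAE found directly or possibly related and an unreasonable risk then leads to suspension under 8.6.8 itself. One the Sponsor finds unrelated falls to the second bullet, where section 15 still controls.

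Merely sending the uncovered cases to section 15 would be weaker. Section 15 does not carry the immediate all-site suspension, the specified notifications or the condition for resuming that the first bullet provides.

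The cost is a short protocol amendment, with IRB approval and regulatory approval if applicable (section 12.3), and possibly a slightly more frequent study-wide pause. Visits, sample size and analysis do not change.
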